6.3.2 Blinding and Masking Procedures

As both arms are receiving remdesivir, the remdesivir product is not blinded and study infusions can be labeled accordingly.

The baricitinib/placebo component is blinded. Baricitinib and placebo tablets are identical in appearance.

Unblinding of the study will occur after all subjects enrolled have reached the end of study, and these visits are monitored and data is cleaned, or if the DSMB recommends unblinding.

If AEs occur and investigators are concerned about the treatment allocation, the treatment can be discontinued. If a Serious Adverse Event occurs, that is thought to be related to the study drug, and the treating clinician believes that knowledge of the treatment arm may change the therapy provided to the patient, the individual subject can be unblinded. The procedure for unblinding will be further detailed in the Manual of Operations.

6.4 Study Intervention Compliance

Each dose of study product will be administered by a member of the clinical research team who is qualified and licensed to administer the study product. Administration and date, and time, will be entered into the case report form (CRF).

6.5 Concomitant Therapy

6.5.1 Permitted Concomitant Therapy and Procedures

Receipt of any exclusionary treatments or medications prior to screening will be assessed to determine eligibility as described in the exclusion criteria. This includes use of strong inhibitors of organic anion transporter 3 (OAT3) such as probenecid which are prohibited during the study.

For patients that are eligible for the study, other therapy received prior to enrollment with any other experimental treatment or off-label use of marketed medications that are intended as specific treatment for COVID-19 or the SARS-CoV-2 infection (i.e., post-exposure prophylaxis [PEP]) are permitted but must be discontinued on enrollment. There is no waiting period between discontinuation of these treatments and administration of study products. However, these prior treatments and their end date should be documented on the Concomitant Medication (CCM) form in the Advantage eClinical system.

There are two scenarios in which outpatient experimental treatment or off-label use of marketed medications that are intended as specific treatment for COVID-19 do not need to be discontinued. First, subjects who are taking another antiviral for a concurrent infection (e.g. oseltamivir for an influenza virus, lopinavir/ritonavir for HIV, etc.) or another existing medical condition (e.g. hydroxychloroquine for lupus, etc.) may continue with the treatment. Note that these treatments may be thought of as an off-label medication for COVID-19, however, because they were being used prior to study enrollment for another indication, they are allowable. Second, if there is a written policy or guideline for the local standard of care and treatment of COVID-19 patients or SARS-CoV-2 infection (i.e., not just an individual clinician decision), continuation of these outpatient medications are permitted. This could include lopinavir/ritonavir (Kaletra), hydroxychloroquine or other agents. There should be plans on how the concomitant drugs are stopped in case of additive toxicities.

VTE prophylaxis is recommended for all patients unless there is a major contraindication such as active bleeding events or history of heparin-induced thrombosis.

6.5.2 Prohibited Concomitant Therapy

A subject cannot participate in another clinical trial for the treatment of COVID-19 until after Day 29 (see exclusion criteria).

If there are NO written policies or guidelines for local standard of care and treatment of COVID-19 patients or SARS-CoV-2 infection, concomitant use of any other experimental treatment or

Appendix B - ACTT-2: Baricitinib/Remdesivir vs Remdesivir
off-label use of marketed medications intended as specific treatment for COVID-19 or SARS-CoV-2 infection are prohibited. This includes medications that target the host immune response.

Once enrolled, use of any biologic therapy outside of local written standards of care are prohibited. This includes monoclonal antibodies targeting cytokines (e.g., TNF inhibitors; interleukin-1[IL-1], IL-6 [tocilizumab or sarilumab]), or T-cells (e.g., abatacept); monoclonal antibodies targeting B-cells (e.g., rituximab, and including any targeting multiple cell lines including B-cells); JAK inhibitor(s) other than baricitinib (e.g., imatibib, genfinitib); and interferon, plasma, or immunoglobulin (IgG) therapies for COVID-19.

Strong inhibitors of organic anion transporter 3 (OAT3) such as probenecid are prohibited during the study.

Corticosteroids for the treatment of COVID-19 are prohibited. Several treatment guidelines for COVID-19 recommend against the routine use of systemic corticosteroids for the treatment of COVID-19 in hospitalized, non-critically ill patients. However, corticosteroids are permitted for other standard indications including asthma exacerbation, ARDS, COPD, laryngeal edema, adrenal insufficiency, shock, etc.

There is no available data on potential interactions between remdesivir and other anti-SARS-CoV investigational agents. Administering remdesivir concurrently with other agents may lead to antagonism or synergy or may have no effect.

Concomitant medications will be assessed only from 7 days prior to enrollment to Day 15 or upon discharge, whichever comes first. Report all prescription medications taken during this time period. Record medications once regardless of the number of times it was given during the time period. For example, vasopressors or insulin should be recorded when first started (the start date) and end date if ended before Day 15 or discharge. Dose of medication is not recorded in Advantage eClinical. Record all antipyretics and other medications given for symptomatic care, if they are administered while an inpatient. However, record these medications only once, even if given multiple times, as needed during hospital course. Do not report medications that the subject did not actually receive during study (e.g., prn medications that were never given).

Do not report vitamins, herbal supplements, or topical medications. Do not report over-the-counter cold medicines and antipyretics that the subject reportedly took at home prior to hospitalization. See the MOP for more information about recording concomitant medications.

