1.2 Schedule of Assessments

Table 1. Schedule of Assessments (SOA)

Day +/- Window	Screen	Baseline	Study Intervention Period	Follow-up Visits		
	-1 or 1	1	Daily until hospital discharge	15 ⁷ ± 2	22 ⁷ ± 3	29 ⁷ ± 3
ELIGIBILITY						
Informed consent	X					
Demographics & Medical History	X					
Review SARS-CoV-2 results	X					
STUDY INTERVENTION						
Randomization		X				
Administration of investigational agent			
 • Remdesivir daily infusion until day 10 or discharge. • Baricitinib or placebo: daily by mouth until day 14 or discharge 			
STUDY PROCEDURES						
Targeted physical exam		X				
Vital signs including SpO ₂ ¹		X ⁴	Daily until discharge ⁸	X ⁹		X ⁹
Clinical data collection ²		X ⁴	Daily until discharge ⁸	X ⁹	X ⁹	X ⁹
Adverse event evaluation		X ⁴	Daily until discharge ⁸	X ⁹	X ⁹	X ⁹
Concomitant medication review		X ⁴	From Day -7 to Day 15			
SAFETY LABORATORY						
Safety hematology, chemistry and liver tests	X ³	X ^{4,5,6,7}	Day 3, 5, 8, 11 (all ± 1 day) if hospitalized ^{6,7}	X ⁹		X ⁹
Pregnancy test for females of childbearing potential	X ³					
RESEARCH LABORATORY						
Blood for plasma to test for PCR SARS-CoV-2		X ^{4,6}	Day 3, 5, 8, 11 (all ± 1 day) if hospitalized			
Oropharyngeal swab ¹⁰		X ^{4,6}	Day 3, 5, 8, 11 (all ± 1 day) if hospitalized	X ⁹		X ⁹
Blood for serum (secondary research)		X ^{4,6}	Day 3, 5, 8, 11 (all ± 1 day) if hospitalized	X ⁹		X ⁹

Notes:

¹Vital signs include temperature, systolic blood pressure, heart rate, respiratory rate, O₂ saturation and level of consciousness. Vital signs collected as part of standard care may be used.

²Refer to Section 8.1.2 of the protocol for details of clinical data to be collected including ordinal score, NEWS, oxygen requirement, mechanical ventilator requirement, etc.

³Screening laboratory tests include: CBC with differential (including absolute neutrophil count and absolute lymphocyte count), ALT, AST, creatinine (and calculate an estimated glomerular filtration rate (eGFR) the formula used is determined

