3.2. Endpoints

Primary Endpoint

Time to recovery, where recovery is defined as clinical status in states 1, 2, or 3 of the 8-point ordinal scale, censored at Day 29.

- Clinical status of a subject (8-point ordinal scale) is defined below:
 - 8. Death;
 - 7. Hospitalized, on invasive mechanical ventilation or ECMO;
 - 6. Hospitalized, on non-invasive ventilation or high flow oxygen devices;
 - 5. Hospitalized, requiring supplemental oxygen;
 - 4. Hospitalized, not requiring supplemental oxygen - requiring ongoing medical care (COVID-19 related or otherwise);

3. Hospitalized, not requiring supplemental oxygen - no longer requiring ongoing medical care;
2. Not hospitalized, limitation on activities and/or requiring home oxygen;
1. Not hospitalized, no limitations on activities

Secondary Endpoints

The key secondary endpoint is clinical status (8-point ordinal scale) on Day 15.

The other secondary endpoints are:

- Ordinal outcome assessed daily while hospitalized and on Days 15, 22, and 29.
- NEWS assessed daily while hospitalized and on Days 15 and 29.
- Days of supplemental oxygen (if applicable).
- Days of non-invasive ventilation/high-flow oxygen (if applicable).
- Days of invasive mechanical ventilation/ECMO (if applicable).
- Days of hospitalization.
- Date and cause of death (if applicable).
- SAEs.
- Grade 3 and 4 adverse events
- WBC with differentials, hemoglobin, platelets, creatinine, glucose, total bilirubin, ALT, AST, INR, d-dimer, and CRP on Day 1; Days 3, 5, 8, and 11 (while hospitalized); and Days 15 and 29 (if attends in-person visit or still hospitalized).

Exploratory Endpoint

- Qualitative and quantitative polymerase chain reaction PCR for SARS-CoV-2 in OP swab on Day 1; Days 3, 5, 8, and 11 (while hospitalized); and Days 15 and 29 (if attends in-person visit or still hospitalized).
- Qualitative and quantitative PCR for SARS-CoV-2 in blood on Day 1; Days 3, 5, 8, and 11 (while hospitalized).

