6.4. Covariates and Subgroups

Subgroup analyses for the main efficacy outcomes (i.e. the primary and key secondary analyses) will evaluate the treatment effect across the following subgroups:

- Geographic region:
 - US sites; Non-US sites
 - North American sites; Asian sites; European sites
- Duration of symptoms prior to enrollment
 - Quartiles
 - ≤ 10 days; > 10 days
 - \leq Median; $>$ Median
- Race (White; Black/African American; Asian; Other)
- Comorbidities
 - None; Any
 - None, One, Two or more
 - Obese; Non-Obese
- Age (<40 ; 40-64; 65 and older),
- Sex (Female; Male),
- Severity of disease
 - Randomization stratification: Moderate (ordinal 4/5); Severe (ordinal 6/7).
 - Actual disease severity at baseline: Moderate (ordinal 4/5); Severe (ordinal 6/7)
Note these analyses will only be performed if at least one subject is erroneously randomized into the incorrect disease severity stratum.
 - Baseline ordinal scale category: 4; 5; 6; 7

Additionally, main analyses of all secondary efficacy outcomes will evaluate the treatment effect across the following subgroups:

- Duration of symptoms prior to enrollment (\leq Median; $>$ Median)
- Severity of disease

- Randomization stratification: Moderate (ordinal 4/5); Severe (ordinal 6/7).
- Actual disease severity at baseline: Moderate (ordinal 4/5); Severe (ordinal 6/7)

Note these analyses will only be performed if at least one subject is erroneously randomized into the incorrect disease severity stratum.

- Baseline ordinal scale category: 4; 5; 6; 7

There will also be a sensitivity analysis of the primary, key secondary, and mortality outcomes to evaluate the effect of concomitant therapy including experimental treatment and off-label use of marketed medications that are intended as treatment for COVID-19 and are given to patient prior to and during the study. A blinded review of the concomitant medication data will be performed by the medical monitor to identify medications that fall into any of the following categories of “Medications of Interest”:

- Antivirals
 - Protease inhibitors
 - Polymerase inhibitors
- Potential Treatments for COVID-19
 - Hydroxychloroquine/Chloroquine
 - Other
- Corticosteroids
- Other anti-inflammatory drugs
 - Monoclonal Antibodies Targeting Cytokines
 - Other Biologic Therapies

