Summaries of subjects who report use of the categories and subcategories of therapies/treatments will be provided. Note that after the blinded review of the medications, additional categories/sub-categories may be defined and/or categories/sub-categories may be combined.

In addition, the sensitivity analyses will consider the following categories (individually):

- Any Medication of Interest
- Hydroxychloroquine/Chloroquine
- Corticosteroids
- Other Anti-Inflammatory Drugs

For the recovery analyses, if a subject recovered prior to use of any of the medications/therapies, then the subject will still be counted as a recovery in the sensitivity analysis. For the analysis of the key secondary outcome, if a subject reports use of any of the medications/therapies prior to their Day 15 assessment, then the subject’s last clinical status score prior to medication/therapy use will be used as their Day 15 outcome. For the mortality analyses, subjects will be censored at the time of medication/therapy initiation.

In addition, the effect of treatment on the primary and key secondary efficacy outcomes will be explored via regression modeling controlling for age, duration of symptoms prior to enrollment, baseline d-dimer, and baseline CRP values as continuous covariates.

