In addition, a forest plot will be generated for the “leave one out” sensitivity analyses described in Section 6.7; hazard ratio estimates and CIs will be provided for each subgroup that leaves a single site out.

An additional sensitivity analysis will evaluate the effect of recoveries that were not sustained as indicated in Section 3.3.2.

As noted in Section 6.4, analyses that take into account concomitant medication will be performed. The primary analysis will be repeated, where subjects who take prohibited medications will be treated as treatment failures and will be censored at the time of medication use.

Two corroborative summaries will also be generated. A summary of the number and percentage of subjects in each treatment group who recovered (and are alive), did not recover (and are alive), and died by Day 29 will be summarized. The summary will also include the numbers and percentages, grouping deaths and non-recoveries together (Table 24). The summaries will also be provided by the duration of symptoms categorizations specified in Section 6.4.

Other censoring techniques and additional analyses of the primary outcome may be performed.

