9.1.2. Prior and Concomitant Medications

Medication history (concomitant medications) includes a review of all current medications and medications taken within 7 days prior to enrollment through approximately Day 15 or early termination (if Day 15), whichever occurs first.

Summaries of medications that were started prior to dosing and continued at the time of dosing or started after dosing while on study will be presented by WHO Drug Level 1 and 2 Codes, disease severity, and treatment group (Table 53). Summaries of overall use of prohibited medications/therapies listed in Section 6.4 that were started prior to dosing and continued at the time of dosing or started after dosing while on study as well as use by select study days will also be generated (Table 54 and Table 55).

Individual subject listings will be presented for all concomitant medications (Listing 9).

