The “Disease Severity” and “Analysis Population” columns will be removed. A “Subgroup” column will be inserted to the left of the “Treatment Group” column. These tables will not display the “Any...” rows. For the analysis controlling for age, symptom duration, d-dimer, and CRP values as continuous covariates, the elements for the “Subgroup” column will state “Baseline Predictors as Continuous Covariates”. The elements for the “n” and “Median Time to Recovery” columns will display “-“. P-values will not be included in these tables.

Programming Notes for Tables 22 and 23:

P-values will not be included in these tables.

Table 22 will include a column to the left of the “n” column titled “m”. The corresponding footnote will read “m = Number of subjects readmitted for COVID-19.” Table 11 will include the following footnote: “In this analysis, subjects that recover and are subsequently readmitted for COVID-19 are censored at 28 days”.

Table 23 will include a column to the left of the “n” column titled “m”. The corresponding footnote will read “m = Number of subjects reporting use of the medication of interest.” For Table 12, the “Analysis Population” column will be replaced by a column labeled “Medication of Interest”. Separate models will be fit for the following categories of medications (see Section 6.4):

- Any Medication of Interest
- Hydroxychloroquine/Chloroquine
- Corticosteroids
- Anti-Inflammatory Drugs

The table will include the following footnote: “In this analysis, subjects that reported use of the specified medications of interest (Section 6.4 of the SAP) are censored at time of medication receipt.”

Table 24: Summary of Recoveries and Deaths by Day 29 – ITT Population

Grouping Variable	Subgroup	Treatment Group	Recovered		Did Not Recover		Deaths		Not Recovered or Died	
			n	%	n	%	n	%	n	%
Disease Severity	Moderate	Baricitinib + RDV (N=X)	x	x	x	x	x	x	x	x
		Placebo + RDV (N=X)	x	x	x	x	x	x	x	x
	Severe	Baricitinib + RDV (N=X)	x	x	x	x	x	x	x	x
		Placebo + RDV (N=X)	x	x	x	x	x	x	x	x
	Any Severity	Baricitinib + RDV (N=X)	x	x	x	x	x	x	x	x
		Placebo + RDV (N=X)	x	x	x	x	x	x	x	x
Repeat for duration of symptoms categories in Section 6.4										
N= Number of subjects in the ITT Population.										

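### Medication recording stops at Day 15 or discharge, but the medications-of-interest analyses of recovery and mortality censor at reported use through Day 29, so later first use counts as non-use

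*Protocol*

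**What the plan says.** **Recording window.** Protocol Appendix B 6.5.2 says "Concomitant medications will be assessed only from 7 days prior to enrollment to Day 15 or upon discharge, whichever comes first". The ACTT-2 Schedule of Assessments (Appendix B 1.2) gives the medication review as "From Day -7 to Day 15". Its footnote on follow-up visits does not add a medication review at Day 22, at Day 29 or by phone. SAP 9.1.2 also stops at about Day 15 but names a different alternative end: "through approximately Day 15 or early termination (if Day 15), whichever occurs first".

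**Analyses that use these data.** SAP 6.4 plans sensitivity analyses of the primary, key secondary and mortality outcomes for concomitant therapy, including "off-label use of marketed medications that are intended as treatment for COVID-19 and are given to patient prior to and during the study". The rules are:

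- Recovery: SAP 8.1.2 repeats the primary analysis so that "subjects who take prohibited medications will be treated as treatment failures and will be censored at the time of medication use". The Table 23 footnote says "subjects that reported use of the specified medications of interest (Section 6.4 of the SAP) are censored at time of medication receipt". A recovery before any use is kept (SAP 6.4).
- Mortality: "For the mortality analyses, subjects will be censored at the time of medication/therapy initiation" (SAP 6.4). Table 69 reports time to death at two horizons, Day 15 and Day 29.
- Key secondary: use before the Day 15 assessment means the last score before use is carried to Day 15 (SAP 6.4; medication rows of Table 25).

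**Horizon.** The primary endpoint in SAP 3.2 is time to "clinical status in states 1, 2, or 3 of the 8-point ordinal scale, censored at Day 29".

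**The concern.** Censoring at medication start works only if the start is recorded. After Day 15, or after an earlier discharge, it is not. A subject given a first medication of interest on Day 16 is not censored, stays in the risk set as a non-user, and contributes any later recovery or death to an analysis meant to stop at first use.

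For the recovery analysis this concerns mainly subjects still in hospital after Day 15. Use in that group is foreseeable: section 6.5.2 permits corticosteroids for indications such as ARDS and shock, and corticosteroids are one of the categories analysed separately. A reader of Table 23, or of the Day 29 rows of Table 69, would assume that exposure was observed over the whole period analysed.

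**Working it through.** **1. The plan's own sample size (background; the point does not depend on it).** E = 4(1.96 + z)²/(ln θ)², with z = 1.036 for 85% power and θ = 1.25, gives 722 after rounding up; the plan states 723. Then 723/0.70 = 1032.9; the plan states 1032. With 1:1 allocation that is 516 per arm.

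**2. Recorded time against analysed time.**

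| Item | Source | End |
|---|---|---|
| Medication recording | Protocol App. B 6.5.2 | Day 15 or discharge, whichever is earlier |
| Medication review | App. B Schedule of Assessments | Day 15 |
| Recovery, users censored | SAP 3.2, 8.1.2, Table 23 | Day 29 |
| Mortality, users censored | SAP 6.4, Table 69 | Day 15 and Day 29 |

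Day 1 to Day 29 is 28 days and recording covers at most 14 of them. So 14/28 = 50% of follow-up has no medication recording, and more for a subject discharged before Day 15.

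**3. Who enters the unrecorded period still at risk of recovery.** Inputs are the Day 15 distributions in Appendix B Tables 6 (control) and 8 (treatment, odds ratio 1.75), with 516 subjects per arm. The count is 516 × (control % + treatment %)/100, summed over categories 4 to 7, which leaves out deaths.

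| Scenario | Control, % | Treatment, % | Subjects | Share of 1032 |
|---|---|---|---|---|
| 1 (anticipated) | 1+2+7+8 = 18 | 0.6+1.2+4.3+5.3 = 11.4 | 152 | 15% |
| 2 | 1+1+2+5 = 9 | 0.6+0.6+1.2+3.1 = 5.5 | 75 | 7% |
| 3 | 1+1+5+7 = 14 | 0.6+0.6+3.0+4.4 = 8.6 | 117 | 11% |
| 4 | 1+2+5+17 = 25 | 0.6+1.2+3.1+11.5 = 16.4 | 214 | 21% |
| 5 | 3+4+9+23 = 39 | 1.8+2.5+5.8+17.4 = 27.5 | 343 | 33% |

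These are subjects at risk when recording stops, not subjects misclassified. The misclassified are those among them whose *first* use comes later, and the documents give no rate for that. In the mortality analysis every survivor remains at risk after Day 15, discharged or not, and the same missing rate prevents a count.

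**4. Effect of the discharge cut-off.** Discharge normally counts as recovery, and recoveries before use are kept, so this cut-off matters little for Table 23. It does matter for mortality and for the Day 15 key secondary medication analysis: a subject discharged on Day 6 has no recorded use for the rest of the period to Day 15.

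**The case against.** The strongest case is that this is a labelling matter.

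- *The consequence is limited.* Only sensitivity analyses are touched, and Tables 23 and 69 and the medication rows of Table 25 carry no treatment p-values. This stands.
- *Part of the remedy exists.* Table 69 already has Day 15 rows. This stands. Table 23 has no counterpart.
- *The window looks deliberate.* It follows dosing: Day 15 with a 14-day oral course here, Day 11 with a 10-day course in ACTT-1. That explains the recording but does not justify an analysis that runs beyond it.
- *Other sources may exist.* Prohibited use would be a protocol deviation, and SAP Listing 3 carries the study day. SAP 9.8 speaks of recording medications during the study, and the Manual of Procedures was not available. But the SAP does not feed deviations into the censoring rule, permitted use is not a deviation, and neither SAP 9.8 nor a reference to the Manual overrides the explicit limit in section 6.5.2.

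A reader might infer that everyone unrecovered at Day 15 is misclassified. The documents do not support that: a subject who started in hospital by Day 15 has a recorded date and is censored as planned. The count of unrecovered subjects also includes deaths and subjects who would not recover by Day 29, and it depends on the curve assumed. A constant rate reaching 70% by 28 days leaves exp(−14λ) = 55% unrecovered at 14 days, with λ = −ln(0.3)/28. A front-loaded curve, F(t) = 0.7(1 − e^(−0.1t))/(1 − e^(−2.8)), leaves 42% at 15 days.

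**Conclusion.** The mismatch is real and follows from carrying out both documents as written. First use after Day 15 or discharge is analysed as non-use in Table 23 and in the Day 29 rows of Table 69. It is a minor point: the primary stratified log-rank test and the main key secondary analysis do not depend on it.

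At most 14 of 28 follow-up days are recorded. On the protocol's Day 15 scenarios, 7% to 33% of subjects (15% anticipated) are still at risk of recovery when recording stops. This rests on Tables 6 and 8, on 516 per arm, and on treating categories 4 to 7 at Day 15 as not yet recovered. The number misclassified, and the size and direction of any effect on the hazard ratios, cannot be derived from the documents.

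Two further inferences should be resisted. One is that the Day 15 analyses fit the recorded window completely: they do not for subjects discharged earlier. The other is that the SAP promises to remove the influence of other therapy: section 6.4 says only that it will evaluate the effect.

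**What to change.** 1. Table 23: run the medication analysis with follow-up administratively censored at Day 15.
2. Table 69: name the existing Day 15 rows as the main medication-censored mortality result.
3. Label any Day 29 version of either analysis as not capturing first use after Day 15.
4. Footnote Tables 23, 25 (medication rows) and 69: use after discharge is not recorded, so the Day 15 results are incomplete for subjects discharged earlier.
5. Reconcile the end of recording: discharge in Protocol Appendix B 6.5.2, early termination in SAP 9.1.2.

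The cost is SAP wording, footnotes and one truncated run, with no new data collection. The downside is that these sensitivity analyses then say nothing about Days 16 to 29.
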